### **SUMMARY**

Immediately replacing fibrinogen in perioperative bleeding patients with acquired fibrinogen deficiency improves outcomes. The product that is primarily used for fibrinogen replacement in the US, cryoprecipitate, must be stored frozen and expires six hours after thawing, resulting in a delay in transfusion of approximately 50 minutes from the time it is ordered, as well as unnecessary transfusion of more readily available but not indicated blood components that are transfused while the patients waits for cryo. A modified version of the product, pathogen reduced (PR) cryo, is now FDA approved and can be thawed and stored for 5 days, allowing the product to be available immediately when needed. No clinical studies are available for this product. In this quality improvement study, we will compare the effect that readily available, pre-thawed PR cryo has on transfusion practice in cardiovascular and liver transplant patients who receive PR cryo versus those who receive traditional cryo by randomizing cryo transfusions in the blood bank by month to all cryo or all PR cryo. All clinical decisions, including the need for cryoprecipitate, and laboratory testing will occur per standard of care.

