### INTRODUCTION

Cryoprecipitated AHF product (cryo), a pooled product from 5-10 blood donors, is the primary source of fibrinogen replacement for bleeding patients in the United States. When stored frozen, it has a shelf life of one year; however, it must be thawed prior to use. Thawing, labeling and dispensing cryo can take 28-97 minutes and then it must be transfused within 6 hours due to a theoretical risk of bacterial contamination.

The competing need to have cryo rapidly available for urgent transfusions and the need to avoid wasting product has led to the development of pathogen reduced (PR) cryo, which recently received FDA approval. This product is also called Intercept Fibrinogen Complex (IFC) and can be kept thawed at room temperature for up to 5 days after thawing.

PR cryoprecipitate is derived from a traditional cryoprecipitate product that is treated with amotosalen.

The inactivation of pathogens

[figure not shown]
allows thawed PR cryo to have a shelf-life of 5 days without the risk of microbial contamination. Furthermore, multiple studies have shown that fibrinogen is stable when thawed at room temperature for up to 35 days. The longer shelf-life should reduce product wastage which

would offset the increased cost of PR cryo over traditional cryo. In vitro studies have shown no differences in efficacy between traditional and PR cryo. No safety differences are expected between the two products, as evidenced by the FDA approving PR cryo without any clinical studies.

The same pathogen reduction process used for PR cryo/IFC that was developed by Cerus Corporation has been in use in the United States since 2014 for platelet and plasma products. Cryoprecipitate is a derivative of plasma, and the pathogen reduction process was already FDA approved. Therefore, the FDA approved this blood product and its pathogen inactivation process, without any clinical trials or observational studies.

PR cryo/IFC, the product we are studying, is a biological blood component and the process used to treat PR cryo, known as INTERCEPT® Blood System for Cryoprecipitation (package insert included in IRB application) is the same process used for PR platelets and PR plasma. The pathogen reduction process occurs at the blood supplier and then the product is received by

[figure not shown]

[figure not shown]

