Since PR cryo can be kept at room temperature for 5 days, similar to thawed plasma, the blood bank can opt to have a PR cryo supply thawed and immediately available for use. This can prevent delays in treatment in bleeding patients.

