### **STUDY DESIGN**

Given that PR cryo can be more readily available for urgent perioperative need, the transfusion medicine service and anesthesiologists at NYP/WC would like to transition to this product. PR cryo is a more expensive product, so it is necessary to evaluate whether its availability will reduce the need for other blood products or reduce traditional cryo wastage, prior to fully converting to this product. A single center prospective, pilot cluster randomized study with an adaptive design will be used to compare the availability and cost effectiveness of cryo and PR cryo when it is ordered for standard clinical indications. In this design, the intervention and randomization are not made at the level of the individual patient, but rather on clusters of patients by month. The clusters will include all patients at NYP/WC for whom pooled cryo is ordered during a single month, not just liver transplant and cardiovascular surgery patients.

Since both products are considered clinically equivalent, the blood bank will alternate use of PR cryo and regular cryo each month for all patients with a cryo order over a one year period during the transition to the use of this new product. All patients will receive either traditional cryo or PR cryo in a given month; however, only a subset (CV and LT patients) will be studied.

Data from the EMR and lab systems will be collected from the NYP data warehouse during the one-year QA study and included in the data analysis. The following demographic variables will be collected: age, ethnicity, race, gender, underlying diseases, surgery type, medications given within 5 days of surgery.

The primary outcome will be the total number of blood components (RBCs, platelets, plasma) used over the admission within the first 30 days after surgery.

REDCap will be used for data collection/storage. Our data scientist, who is an Epic Clinical Data Navigator (CDN), will use SQL queries through the NYP Jupiter data warehouse for automated data extractions of clinical and laboratory data. A TRAC request will be submitted once the IRB is approved. Any variables not available through Jupiter will be extracted manually from the electronic medical record by the research coordinator and entered manually in REDCap. We will use the Safe Harbor method for de-identification of data. We will remove all 18 PHI elements referenced by HHS that could identify a patient.

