The secondary outcomes, which are all routinely available in the EMR per standard of care, will include:

1. Number of cryo or fibrinogen concentrate products used perioperatively (defined as anesthesia start time to 3 days post-procedure)

- 2. Number of RBC, plasma, and platelet products used perioperatively (defined as anesthesia start time to 3 days post-procedure)
- 3. Time from OR start time to start of cryo transfusion
- 4. Time from cryo order to start of transfusion
- 5. Number of cryo units wasted by blood bank per month during study periods.
- 6. Laboratory measures, as available in the medical record, related to the indications for cryo: pre and post transfusion FIBTEM amplitude at 10 mins and maximum clot firmness & fibrinogen level within 10 minutes to one hour after the end of the first cryo transfusion.
- 7. Highest and lowest fibrinogen level or ROTEM FIBTEM within 24 hours after surgery.
- 8. Volume in drains (e.g. chest tube for CV surgery) at 24 hours or until removed, whichever is sooner.
- Time from end of bypass pump until end of surgery (reflects time to hemostasis) for CV surgery
- 10. Length of stay (OR, ICU and hospital)
- 11. Need for ventilator
- 12. Time on ventilator
- 13. Overall cost of cryo vs PR cryo, when factoring wastage, during each 1-month period
- 14. Adverse events: fevers, infections, transfusion reactions within 5 days of surgery start time, need for surgical re-exploration, multiorgan system failure
- 15. Fibrinogen level most proximal to end of procedure

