#### **EVALUATION OF PRODUCT SUPERIORITY**

The primary outcome of total number of blood components (RBCs, platelets, plasma) used over the admission within the first 30 days after surgery will be evaluated using a two-sample t-test on the log-transformed values or the Wilcoxon rank-sum test if the log-transform does not result in an acceptable comparability to a normal distribution. This will be based on an intent-to-treat paradigm (all subjects randomized will be evaluated and in the group they were randomized to). However, it is assumed that all of the subjects will be appropriately evaluated for this endpoint.

There are a number of secondary endpoints, and the specific statistical method is indicated below:

- 1. Number of cryo or fibrinogen concentrate products used perioperatively (defined as anesthesia start to 24 hours post-procedure): Wilcoxon rank-sum test
- 2. Number of RBC, plasma, and platelet products used perioperatively (defined as anesthesia start to 24 hours post-procedure): Wilcoxon rank-sum test
- 3. Time from cryo order to ready in the blood bank: Wilcoxon rank-sum test
- 4. Time from cryo order to start of infusion: Wilcoxon rank-sum test
- 5. Number of cryo units wasted by blood bank per day during study periods: Wilcoxon rank-sum test
- 6. Laboratory measures for cryo and PR cryo (pre and post transfusion FIBTEM amplitude at 10 mins and maximum clot firmness, fibrinogen): Wilcoxon rank-sum test
- 7. Volume in mediastinal drains (e.g. chest tube for CV surgery) at 24 hours (or until removed): Wilcoxon rank-sum test
- 8. Length of stay (OR, ICU and hospital) & time on ventilator: log-rank test, particularly if there is any censoring
- 9. Overall cost of cryo vs PR cryo, when factoring wastage, during each 1-month period: Wilcoxon rank-sum test
- 10. Fibrinogen level most proximal to end of procedure, with adjustment for fibrinogen dose administered (if known): without adjustment the Wilcoxon rank-sum test can be used; with adjustment a properly selected linear model (depending on the link function required)

[figure not shown]
In order to control statistical significance for this number of endpoints, the Holm procedure will be used.

[figure not shown]
Many of the endpoints noted above can be evaluated after adjustment with selected covariates using a properly selected linear model (depending on the link function required).

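### Wastage is tested by ranking single days, although the protocol defines it per month and the conversion decision depends on total units wasted

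*Combined protocol and SAP*

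**What the plan says.** All references are to the combined protocol and SAP.

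- Evaluation of Product Superiority, item 5: "Number of cryo units wasted by blood bank per day during study periods: Wilcoxon rank-sum test".
- Secondary outcomes list under Study Design, item 5: "Number of cryo units wasted by blood bank per month during study periods". This is the same outcome in a different unit.
- Evaluation of Product Superiority, item 9: "Overall cost of cryo vs PR cryo, when factoring wastage, during each 1-month period: Wilcoxon rank-sum test". Cost is already a monthly quantity.
- Study Design, on why wastage matters: because PR cryo costs more, "it is necessary to evaluate whether its availability will reduce the need for other blood products or reduce traditional cryo wastage" before full conversion. The Introduction expects lower wastage to offset the higher price.
- Handling of the products: traditional cryo "must be stored frozen and expires six hours after thawing" (Summary). PR cryo "can be kept thawed at room temperature for up to 5 days after thawing" (Introduction), and "the blood bank can opt to have a PR cryo supply thawed and immediately available for use".

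No mean, total, ratio or confidence interval is specified for either item. No wastage rate, share of zero-waste days or stock size is given. Holm's procedure covers the listed endpoints.

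**The concern.** The price offset depends on how many units are lost. A rank-sum test on days addresses a different question: whether a random day under one product tends to rank above a random day under the other. When most days are zero, that ordering mainly reflects how often anything is wasted.

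The storage rules make different patterns plausible. A product that expires six hours after thawing tends to be lost order by order. A thawed stock with a five-day life can expire several pools at a time. If PR cryo is discarded less often but in larger lots, the daily test can call it less wasteful when it wastes as much or more. That would be a wrong answer on one of the two stated grounds for conversion.

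Separately, the product is assigned by calendar month. A day-level test treats days within a month as independent replicates, which they are not.

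**Working it through.** **Inputs.** The plan states no rate, effect or power for wastage, so there is no figure of its own to reproduce. Every wastage pattern below is an assumption. Study Design gives one year ("for all patients with a cryo order over a one year period"), while Study Patient Population refers to two years. Split equally between products, that is about 180 or 360 days (6 or 12 months) per arm. If the ten numbered secondary endpoints form the Holm family, its first step is 0.05/10 = 0.005.

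**1. What the daily test responds to.** Suppose conventional cryo wastes 1 pool on 30% of days and PR cryo wastes 3 pools on 10%.

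- Means: 0.30 × 1 = 0.30 and 0.10 × 3 = 0.30 pools per day, so they are equal.
- P(conventional day ranks higher) = 0.30 × 0.90 = 0.27. P(PR day ranks higher) = 0.10. The rest, 0.70 × 0.90 = 0.63, are ties.
- At 180 days per arm the expected shift in the rank-sum statistic is (0.27 − 0.10)/2 × 180² = 2,754.
- Expected ties are 126 + 162 = 288 zeros, 54 ones and 18 threes. The tie factor is 1 − [(288³ − 288) + (54³ − 54) + (18³ − 18)]/(360³ − 360) = 0.4845.
- SD = √(180² × 361/12 × 0.4845) = 687, so z = 2,754/687 = 4.0. The chance of p<0.05 in favour of PR cryo is about Φ(4.0 − 1.96) = 98%. At 360 days z is about 4.0 × √2 = 5.7, and the chance is about 100%.
- With PR lots of 4 or 5 pools, PR wastes 33% or 67% more (0.40 or 0.50 per day), but 0.27 and 0.10 do not change, because a lot of 3 already outranks every conventional day.

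**2. Simulated patterns** (2,000 runs, independent days, lot size 1 + Poisson). Chance that the daily test declares PR cryo less wasteful at p<0.05:

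| Conventional v PR (share of days × mean units) | Mean waste | 180 days | 360 days |
|---|---|---|---|
| 30% × 1 v 10% × 3 | equal | 98.6% | 100% |
| 40% × 1 v 20% × 2 | equal | 86.6% | 99.0% |
| 20% × 1 v 10% × 2 | equal | 65.2% | 90.8% |
| 30% × 1.5 v 10% × 6 | PR 33% higher | 98.1% | 100% |
| 30% × 1 v 10% × 6 | PR double | 98.4% | 100% |

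In the first row at p<0.005 the rates are 91.3% and 99.9%.

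**3. A stock model instead of assumed lots.** PR pools are used first-in-first-out with a 5-day life and Poisson demand. Conventional cryo wastes 0 or 1 pool per day at the same mean. Wrong-direction rate at 180 days per arm:

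| Demand (pools/day) | Threshold | Stock 4 | Stock 6 | Stock 8 |
|---|---|---|---|---|
| 1 | p<0.05 | 10% | 35% | 60% |
| 1 | p<0.005 | 2% | 12% | 28% |
| 2.5 | p<0.05 | 0% | 5% | 18% |

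At 360 days with a stock of 8 and demand of 1, the rate is about 85% at p<0.05. Discarded lots in such a model average only 1.2 to 1.6 pools.

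**4. The same data by month.** In the first row of step 2 at 180 days, the rate falls from 98.6% to 3.0% with a rank-sum test on monthly totals (6 v 6), and to 4.2% with a large-sample test of mean units per day. Across the patterns in step 2, neither alternative exceeds 5.0%. In the stock model a comparison of monthly totals gives about 2% to 5% where waste is not negligible.

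**5. Does the daily test ignore amount?** With equal frequency in both arms and 1 v 3 units per wastage day, it finds the larger amount in 12% / 21% of runs (180 / 360 days) when waste occurs on 20% of days, 72% / 95% on 40%, and 100% on 60%. With identical distributions it rejects in about 2.5% of runs in each direction.

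**The case against.** Four things can fairly be said for the plan.

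- **The outcome list already says per month.** Read that way, the reversal largely disappears. This stands, and it is why the conflict of units comes first. But the only passage that names a test says per day, and it is the one an analyst would follow.
- **The rank test does use amount.** A reader might infer that it sees only how often product is wasted. Step 5 shows otherwise: once waste occurs on about 40% of days or more, differences in amount are detected well. The problem belongs to data with many zero days.
- **The extreme rates need large lots.** Rates of 98% to 100% assume PR lots of about three pools or more, which the stock model does not produce. Demand also matters. The Interim Analysis section expects 302 study patients in about a year (302/365 = 0.83 per day), each with at least one pool, and other patients draw on the same supply, so demand well above 1 pool per day is plausible and lowers the rate. Single-pool conventional waste is an assumption too, since several thawed pools could be discarded together after massive bleeding. Holding a thawed stock is described as an option. All of this stands and limits the size of the point.
- **Item 9 is monthly.** A reader might infer that the cost comparison can reverse in the same way. It is not a zero-heavy daily count, and nothing in the documents supports that. What remains is that a rank test gives no mean cost difference.

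**Conclusion.** The point holds in limited form. The per-day and per-month definitions of wastage contradict each other. The daily version does not test mean or total wastage and disregards assignment by month.

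Whether it would mislead depends on the wastage pattern, which the documents do not report. At equal mean waste and p<0.05, the stock model (4 to 8 pools, demand of 1 to 2.5 per day) puts the wrong-direction rate at about 0% to 60% for 180 days per arm and 0% to 85% for 360, and lower at the Holm first step. Only the assumed pattern of large, rare PR lots brings it to 98% to 100%, and under that pattern it persists when PR cryo wastes more. These runs take days as independent.

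The documents do not support the stronger conclusion that PR cryo will be falsely declared less wasteful. This is a secondary endpoint, but it informs a stated ground for conversion, so the sponsor should correct it.

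**What to change.** 1. Reconcile the two definitions of item 5 by making the month the unit in both places, and drop the daily rank test.
2. Compare mean units wasted per month, as a difference or ratio with a 95% CI. Take the p-value from a permutation of the month labels as they were actually randomised. With six months per product fixed in advance there are 924 allocations, so the smallest two-sided p-value is 2/924 = 0.002, below the Holm first step of 0.005. Study Design speaks of alternating months and the statistical section of re-randomising each month. The permutation set depends on which was done, so the SAP should state it; strict alternation allows only two sequences and no useful permutation test.
3. For item 9, add the mean monthly cost difference with a 95% CI.

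The cost is SAP wording only, with the same data. The small downside is that, with about 6 to 12 months per arm, a mean is more sensitive to one outlying month. Listing the monthly totals by product would show this.

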# **LABORATORY TESTING**

Patients requiring transfusions intraoperatively or post-operatively are currently already assessed via ROTEM pre and post product transfusions to guide product selection for clinical purposes. A ROTEM transfusion algorithm is already in use for both cardiovascular surgery and liver transplant. All laboratory testing will be standard of care for labs and ROTEM. Patients will have a ROTEM performed on the ROTEM Delta instrument either in the blood bank or in the OR.

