if it is not properly accounted for in the analysis. This study will use randomization between intervention arms each month with a design known as the cluster randomized trial. This allows for the ability to assure that all research subjects in a given month will receive a particular cryo product and ensure the reduction in contamination of the two study arms (one of the primary reasons for designing studies in this fashion). In the planned trial, each month the Weill Cornell blood bank will be randomized to one of the two cryoprecipitates as part of a quality improvement study, the randomized product will be used as standard institutional policy for an entire calendar month. At the end of each month, the blood bank is re-randomized to a new standard policy that is used for the subsequent calendar month. This design is methodologically rigorous and tests the effect of a change in standard policy as it would actually be used in the clinical setting.

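### Secondary endpoint 10 does not say whether the dose-adjusted or the unadjusted fibrinogen comparison counts, and the dose-adjusted one may be biased if dose differs by arm

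*Combined protocol and SAP*

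**What the plan says.** Item 10 of the secondary endpoints in EVALUATION OF PRODUCT SUPERIORITY names end-of-procedure fibrinogen "with adjustment for fibrinogen dose administered (if known". It then gives two methods: "without adjustment the Wilcoxon rank-sum test can be used; with adjustment a properly selected linear model", with the link function left open. Item 15 of the secondary outcomes in STUDY DESIGN lists the same endpoint with no adjustment: "Fibrinogen level most proximal to end of procedure". The Holm procedure is to control significance across the endpoints, but nothing says which of the two item 10 analyses enters it. No target of estimation is stated, whether the total effect of the product policy or the effect at equal dose.

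On timing, the RATIONALE section says that "each month the Weill Cornell blood bank will be randomized to one of the two cryoprecipitates". Dose comes later. CONSENT places the decision to give cryo during hemorrhage in surgery. STUDY PATIENT POPULATION describes ROTEM-guided, goal-directed therapy in both services, and LABORATORY TESTING says patients are "currently already assessed via ROTEM pre and post product transfusions to guide product selection". A related quantity is compared between arms as an outcome in item 1: "Number of cryo or fibrinogen concentrate products used perioperatively (defined as anesthesia start to 24 hours post-procedure): Wilcoxon rank-sum test".

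**The concern.** There are two linked problems.

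The first needs no assumption about the data. One endpoint has two analyses that answer different questions, and the plan does not rank them, so the choice could be made after both results are seen.

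The second is conditional. Dose is set after assignment and shares a cause with the endpoint: patients who bleed more tend to have lower fibrinogen and to be given more. If immediate availability also changes how much is given, adjusting for dose does two things. It removes the part of the policy effect that acts through dose, and it makes patients at the same dose in the two arms differ in bleeding severity.

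At stake is how an adjusted difference would be read. It looks like evidence on the potency of PR cryo per unit given, for a product that the SUMMARY says has no clinical studies.

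**Working it through.** **The plan's own figure.** The documents give no figure for this endpoint. Their one sample-size result, 251 per group, belongs to the primary endpoint. It reproduces from the inputs in SAMPLE SIZE ANALYSIS: log-scale SD = √ln(1 + 1.1²) = 0.8905; difference = |ln 0.8| = 0.2231; n = 2 × [0.8905 × (1.960 + 0.842) / 0.2231]² = 250 by the normal formula, and 251 with the noncentral t (power 0.8001). Nothing below changes it.

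**Algebra.** Let A be arm, U unmeasured bleeding severity (variance 1), and dose have within-arm variance 1:

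- dose = a·A + g·U + error
- fibrinogen = τ·A + b·dose − c·U + error

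Given dose and arm, the expected value of U is g × (dose − a·A). Substituting:

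- dose-adjusted arm coefficient = τ + a·c·g
- total effect of arm = τ + a·b
- bias for the equal-dose effect = a·c·g
- departure from the total effect = a·(c·g − b)

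Both errors are zero when a = 0, that is, when arm does not shift dose. If dose is unrelated to severity (g = 0), the adjusted coefficient is right for the equal-dose effect but still not for the total effect.

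**Illustration in mg/dL (all values assumed).** U ~ N(0,1); dose = 2 + U + a·A + noise of variance 0.5; fibrinogen = 200 − 40U + 20 × dose. There is no product difference at equal dose. Within-arm dose variance is 1 + 0.5 = 1.5, so the expected U given dose and arm is (dose − 2 − a·A)/1.5. Then:

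- dose coefficient = 20 − 40/1.5 = −6.7
- adjusted arm coefficient = (40/1.5) × a = 26.7a
- total effect = 20a

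Halving the slope of dose on severity, with dose variance kept at 1.5, gives an adjusted coefficient of 40 × (0.5/1.5) × a = 13.3a.

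| Arm shift in dose (a) | Total effect | Adjusted, severity slope 1 | Adjusted, severity slope 0.5 | True equal-dose effect |
|---|---|---|---|---|
| 0 | 0 | 0 | 0 | 0 |
| 0.1 | 2.0 | 2.7 | 1.3 | 0 |
| 0.5 | 10.0 | 13.3 | 6.7 | 0 |
| −0.5 | −10.0 | −13.3 | −6.7 | 0 |

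Least squares on 2,000,000 simulated patients (slope 1, a = 0.5) gave +13.4 adjusted, −6.7 for dose and +10.0 unadjusted. With a = −0.5 the adjusted and unadjusted values were −13.3 and −10.0. A shift of 0.5 is 0.5/√1.5 = 0.41 within-arm SD, and severity explains 1/1.5 = 67% of within-arm dose variance, so the slope-1 column assumes strong confounding.

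**Second illustration, in SD units (also assumed).** With b = 0.4, τ = 0, residual SD 0.7 and a = −0.3, the total effect is −0.3 × 0.4 = −0.120. The adjusted coefficient is −0.027 (g = c = 0.3), −0.108 (g = c = 0.6) or −0.192 (g = c = 0.8). It can therefore understate or overstate the total effect.

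With 251 independent patients per arm, g = c = 0.6 and no equal-dose effect, the adjusted test at the 5% level rejected in these proportions of 4,000 simulated trials: 5.0% at a = 0, 15% at −0.2, 28% at −0.3 and 63% at −0.5.

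**The case against.** The strongest reply is that the unadjusted comparison is already in the plan and that the bias is hypothetical. Much of this stands.

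- **The plan is not committed to the adjusted analysis.** A reader might infer from the endpoint's name that dose adjustment is settled. It is not: the same item says "without adjustment the Wilcoxon rank-sum test can be used", and the STUDY DESIGN list has no adjustment. The firm defect is that neither analysis is named as the one that counts.
- **Dose is not documented to differ by arm.** A reader might infer that availability changes dose and that the adjusted difference is therefore biased. The documents predict effects on delay, other blood components, wastage and cost, not on fibrinogen dose, and they treat the products as clinically equivalent. Equivalent products can still be given in different amounts when one is ready at once and the other takes about 50 minutes, so a dose difference is plausible, but no more than that. Item 1 is only a related measure: it counts products, and its window runs past the end of the procedure.
- **The condition that dose be known is ambiguous.** It could restrict the model to patients with a recorded dose. It could equally mean adjusting only if dose data can be obtained at all. Patient-level selection cannot be taken as planned.
- **Response at equal dose is a legitimate question.** It needs severity control, however. The section allows covariate adjustment in general, and EQUIVALENCY BETWEEN COHORTS names MELD and EUROSCORE. Those scores are there to check that the groups are similar, are not named in the item 10 model, and are at most partial proxies for bleeding during surgery.
- **The impact is limited.** This is one secondary endpoint in a study described as a pilot.

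**Conclusion.** The point holds in conditional form. It is certain that item 10 offers two analyses and does not say which is reported or enters the Holm procedure. It is also clear that dose follows assignment and is tied to bleeding and ROTEM results. If dose differs by arm, the adjusted difference may be biased: it generally does not give the total policy effect, and without control for intraoperative severity it does not give a clean equal-dose effect. If dose does not differ by arm, both linear models above show no bias.

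The size cannot be computed from the documents. The figures of 0, 2.7 and 13.3 mg/dL at shifts of 0, 0.1 and 0.5 rest wholly on assumed values, and they halve if the severity slope is halved. They show that the error can matter, not that it will. The primary endpoint and the 251 per group are untouched.

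**What to change.** State in item 10 that the comparison not adjusted for dose, in all analysed patients with an end-of-procedure fibrinogen value, is the reported result and the one entered in the Holm procedure. This also brings the item into line with the STUDY DESIGN list. Keep the dose-adjusted model as an exploratory analysis, labelled as conditioning on a post-assignment variable, and state the assumptions on bleeding severity under which it could be read as an equal-dose effect. Say what the condition that dose be known means: a rule for patients, or a rule for whether the model is fitted at all.

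The cost is wording only. The downside is that the main result no longer speaks to fibrinogen response per unit dose, which moves to the exploratory analysis.

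The change does not cure a separate issue. The inclusion and exclusion criteria restrict the study to patients who received cryo in surgery and at least one pool of it, so even the unadjusted comparison is made in patients selected on something that happens after assignment.
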